Appendix 12. Example SAS Code for Analyses OF Dose-Response Models

This code has been included as an example to show possible ways of fitting an Emax model and in SAS. The actual code may be adjusted, depending on the testing of programming and the data. No SAP amendment is needed if the actual code is different from the example code in this section. The common procedure of PROC NLMIXED has been used. Therefore, PROC NLMIXED has also been used as the ESTIMATE statement allows you to specify the contrast of interest. As our decision criteria are based on differences in proportions this procedure allows us to back transform and express the data in this format. The following code was written assuming the format of the input dataset is of the form:

DOSE	LNDOSE	COUNT	N
0	-9.2103	5	30
10	2.3025	9	30
303.4012	11	30	
100	4.6052	18	30
200	5.2983	21	30

where

DOSE=DOSE in mg,
LNDOSE=log(DOSE+0.0001)
COUNT=number of responses,
N=number of subjects

/* SAS example code */

*** Model 1: EMAX MODEL without covariate ***;

**Degrees of freedom is number of subjects-number of parameters (3);
proc nlmixed data=resp alpha=0.1 df=&df;

** specify that ed50 must be positive;
bounds ed50>0;

eta = e0 + ((emax*dose)/(ed50+dose));
expeta = exp(eta);
p = expeta/(1+expeta);

model count ~ binomial(n,p);

** LOG(ODDS RATIOS) - TAKE EXP(ESIMATE) and EXP(CI) TO CALCULATE PARAMETER AND 60% CI FOR MAIN BODY TABLE;

** ACTUAL ESTIMATED PROPORTIONS ;

estimate 'Model 1: Actual proportions 200mg'
exp(e0 + (emax*200/(ed50+200)))/(1 + exp(e0_int + (emax*200/(ed50+200))));

estimate 'Model 1: Actual proportions 100mg'

$\exp(e_0 + (e_{max} * 100 / (ed50 + 100))) / (1 + \exp(e_0_int + (e_{max} * 100 / (ed50 + 100))))$;

estimate 'Model 1: Actual proportions 30mg'

$\exp(e_0 + (e_{max} * 30 / (ed50 + 30))) / (1 + \exp(e_0_int + (e_{max} * 30 / (ed50 + 30))))$;

estimate 'Model 1: Actual proportions 10mg'

$\exp(e_0 + (e_{max} * 10 / (ed50 + 10))) / (1 + \exp(e_0_int + (e_{max} * 10 / (ed50 + 10))))$;

estimate 'Model 1: Actual proportions 0mg'

$\exp(e_0) / (1 + \exp(e_0_int))$;

** Differences among ACTUAL ESTIMATED PROPORTIONS ;

estimate 'Model 1: proportion difference 200mg vs. placebo'

$\exp(e_0 + (e_{max} * 200 / (ed50 + 200))) / (1 + \exp(e_0_int + (e_{max} * 200 / (ed50 + 200)))) - \exp(e_0) / (1 + \exp(e_0_int))$;

estimate 'Model 1: proportion difference 100mg vs. placebo'

$\exp(e_0 + (e_{max} * 100 / (ed50 + 100))) / (1 + \exp(e_0_int + (e_{max} * 100 / (ed50 + 100)))) - \exp(e_0) / (1 + \exp(e_0_int))$;

estimate 'Model 1: proportions difference 30mg vs. placebo'

$\exp(e_0 + (e_{max} * 30 / (ed50 + 30))) / (1 + \exp(e_0_int + (e_{max} * 30 / (ed50 + 30)))) - \exp(e_0) / (1 + \exp(e_0_int))$;

estimate 'Model 1: proportion difference 10mg vs. placebo'

$\exp(e_0 + (e_{max} * 10 / (ed50 + 10))) / (1 + \exp(e_0_int + (e_{max} * 10 / (ed50 + 10)))) - \exp(e_0) / (1 + \exp(e_0_int))$;

ods output AdditionalEstimates=est

FitStatistics=loglike

ParameterEstimates=parms;

run;

Appendix 13. Estimate and Confidence Interval for Risk Difference (Proportion Difference) Using GLIMMIX Procedure with link=logit

It is known that the estimate and CI on the logit scale can be obtained using GLIMMIX procedure with dist=binary and link=logit; and using link option in GLIMMIX will generate the estimate for proportions. The variance of risk difference (proportion difference) cannot be directly obtained by GLIMMIX procedure using link=logit. This appendix describes how to obtain the estimate and the confidence interval (CI) for risk difference (proportion difference) by delta method.

Suppose that p_1 and p_2 are the two proportions of interest. $l_1 = \log \text{it}(p_1) = \log\left(\frac{p_1}{1-p_1}\right)$ and

$l_2 = \log \text{it}(p_2) = \log\left(\frac{p_2}{1-p_2}\right)$ are the logit for the two proportions. Note that the l_1, l_2, p_1

and p_2 can be obtained by GLIMMIX procedure, and so are the covariance matrix for l_1 and l_2 . Our interest is to derive the variance of $p_1 - p_2$.

Denote that $f(l_1, l_2) = \frac{e^{l_1}}{1+e^{l_1}} - \frac{e^{l_2}}{1+e^{l_2}} = p_1 - p_2$. A Taylor series expansion of $f(l_1, l_2)$ about the values (l_{10}, l_{20}) is given by:

$$f(l_1, l_2) = f(l_{10}, l_{20}) + \frac{\partial f(l_1, l_2)}{\partial l_1} \Big|_{(l_{10}, l_{20})} (l_1 - l_{10}) + \frac{\partial f(l_1, l_2)}{\partial l_2} \Big|_{(l_{10}, l_{20})} (l_2 - l_{20}) + (2\text{nd or higher order terms}).$$

Therefore

$$\begin{aligned} \text{Var}(f(l_1, l_2)) &\approx \left[\frac{\partial f(l_1, l_2)}{\partial l_1} \Big|_{(l_{10}, l_{20})} \right]^2 \text{Var}(l_1) + \left[\frac{\partial f(l_1, l_2)}{\partial l_2} \Big|_{(l_{10}, l_{20})} \right]^2 \text{Var}(l_2) \\ &+ 2 \left[\frac{\partial f(l_1, l_2)}{\partial l_1} \Big|_{(l_{10}, l_{20})} \right] \left[\frac{\partial f(l_1, l_2)}{\partial l_2} \Big|_{(l_{10}, l_{20})} \right] \text{Cov}(l_1, l_2) \end{aligned} \tag{1}$$

Since

$$\frac{\partial f(l_1, l_2)}{\partial l_1} = \frac{e^{l_1}}{(1+e^{l_1})^2} \text{ and } \frac{\partial f(l_1, l_2)}{\partial l_2} = -\frac{e^{l_2}}{(1+e^{l_2})^2},$$

$$\begin{aligned} \text{Var}(f(l_1, l_2)) &\approx \left[\frac{e^{l_1}}{(1+e^{l_1})^2} \right]^2 \text{Var}(l_1) + \left[\frac{e^{l_2}}{(1+e^{l_2})^2} \right]^2 \text{Var}(l_2) \\ &- 2 \left[\frac{e^{l_1}}{(1+e^{l_1})^2} \right] \left[\frac{e^{l_2}}{(1+e^{l_2})^2} \right] \text{Cov}(l_1, l_2) \end{aligned} \tag{2}$$

Now take $(l_{10}, l_{20}) = (\hat{l}_1, \hat{l}_2)$ where (\hat{l}_1, \hat{l}_2) are the estimates of logits which are obtained by GLIMMIX procedure. Then by analogy with the above result, the corresponding estimated variance of the estimator is given by

$$\begin{aligned} \hat{Var}(f(\hat{l}_1, \hat{l}_2)) &\approx \left[\frac{e^{\hat{l}_1}}{(1+e^{\hat{l}_1})^2} \right]^2 Var(\hat{l}_1) + \left[\frac{e^{\hat{l}_2}}{(1+e^{\hat{l}_2})^2} \right]^2 Var(\hat{l}_2) \\ &- 2 \left[\frac{e^{\hat{l}_1}}{(1+e^{\hat{l}_1})^2} \right] \left[\frac{e^{\hat{l}_2}}{(1+e^{\hat{l}_2})^2} \right] Cov(\hat{l}_1, \hat{l}_2) \end{aligned} \tag{3}$$

In conclusion, using GLIMMIX the estimates of logit, variance of the estimate and the corresponding CI for $p_1 - p_2$ can be written as

$$\begin{aligned} \hat{p}_1 - \hat{p}_2 &= \frac{e^{\hat{l}_1}}{1+e^{\hat{l}_1}} - \frac{e^{\hat{l}_2}}{1+e^{\hat{l}_2}}; \\ \hat{Var}(\hat{p}_1 - \hat{p}_2) &= \hat{Var}(f(\hat{l}_1, \hat{l}_2)); \\ (1-\alpha)\%CI : \hat{p}_1 - \hat{p}_2 &\pm z_{1-\alpha/2} \sqrt{\hat{Var}(\hat{p}_1 - \hat{p}_2)} \end{aligned} \tag{4}$$

Where $\hat{Var}(f(\hat{l}_1, \hat{l}_2))$ is given in (3).

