4.2. Decision Rules

4.2.1. Dose Response Modeling

A three-parameter Emax model will be employed for dose-response fitting for the primary endpoint (IGA response at Week 12). If a monotonic dose-response curve is detected, then model estimates and the corresponding treatment effect along with 95% confidence intervals will be reported.

If the data do not support an Emax model, the decision rule may be based on pairwise comparison analysis.

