4.2.2. Multiplicity Adjustment

The multiplicity adjustments are considered only in the analysis of the primary endpoint when the Emax model does not fit. Hochberg method (Hochberg, 1988) is used to account for that the null hypothesis will be rejected if a treatment effect is detected at Week 12. The overall Type I family-wise error rate (FWER) is controlled at 0.05 (one-sided).

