8.1.1.1. Primary Analysis

The primary analysis is the analysis of the primary endpoint, IGA clear (0) or almost clear (1) and ≥ 2 points improvements at Week 12, based on the FAS population. NR approach will be used to handle missing values as described in [Section 7.1](#).

IGA response at Week 12 will be analyzed using the Emax dose-response model. The estimation of E_0 , E_{max} and ED_{50} will be reported in mean, standard deviation and 95% CI. These can be implemented by using PROC NL MIXED in SAS.

The three parameter Emax model is a non-linear equation such that the expected response E with or without baseline disease severity in the model can be written as:

$$E = E_0 + \frac{E_{max} Dose}{ED_{50} + Dose}$$

Where:

E is the logit function for the log odds of response $Logit(p)$.

E_0 is in placebo IGA response.

E_{max} is the difference between maximum achievable response (at infinite dose) and baseline.

ED_{50} is the dose that produces half maximal effect ($E_0 + E_{max}/2$).

The 3-parameter Emax model describes a dose response that starts at E_0 and smoothly increases to an asymptote. The fitted curve will be graphically displayed with 95% confidence band. Model based estimation of treatment effect for each dose compared to placebo will be presented with 95% confidence interval.

Sensitivity analyses for IGA will be performed with generalized linear mixed models (GLMM) on FAS population with OC. Fixed factors include treatment, covariates (baseline disease severity such as EASI score), visit and treatment by visit interaction. Random effect includes random intercept for each subject. These can be implemented with SAS PROC GLIMMIX. P-values and inference for odds ratios between treatments will be provided based on the link function of logit. A delta method will be used to obtain 90% confidence intervals

for the risk differences. The overall p-value for treatment effect at each time point may be also presented. In addition, logistic regression analysis including treatment, covariates (baseline disease severity) at each time point will be performed on FAS with NR missing value imputation.

When an Emax model does not adequately capture the dose-response relationship or the Emax model does not converge, analysis from GLMM on FAS with OC and/or logistic regression on FAS with NR imputation may be considered for decision making to characterize the dose-response with dose being considered as a continuous variable.

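### The example code for the primary Emax analysis sets 90% limits where the SAP text specifies 95%, and its nine ESTIMATE statements use a parameter the model does not define

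*SAP*

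**What the plan says.** The SAP text is consistent. Section 4.2.1 says that, if a monotonic dose response is found, "model estimates and the corresponding treatment effect along with 95% confidence intervals will be reported". Section 8.1.1.1 gives 95% intervals for E0, Emax and ED50. It adds "The fitted curve will be graphically displayed with 95% confidence band" and "Model based estimation of treatment effect for each dose compared to placebo will be presented with 95% confidence interval".

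Appendix 12, the only code given for this model, differs in three places:

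- The procedure call contains "data=resp alpha=0.1". No ESTIMATE statement sets its own level.
- A comment about exponentiating log odds ratios says "TO CALCULATE PARAMETER AND 60% CI FOR MAIN BODY TABLE". No log odds ratio statement follows it.
- The linear predictor is built from e0, emax and ed50. The ESTIMATE statements for the response proportions and for the differences from placebo use e0 in the numerator and e0_int in the denominator.

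The appendix is presented as an example, and it states: "No SAP amendment is needed if the actual code is different from the example code in this section". It also says that the decision criteria are on the scale of differences in proportions, which is the scale of the affected statements.

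**The concern.** The Emax fit is the primary analysis, and the dose-versus-placebo differences are its main product. A programmer who starts from Appendix 12 and keeps the procedure call would produce 90% limits for tables and figures that the SAP says carry 95% limits. Nothing in the output would look wrong, because the estimates are unaffected and only the limits move.

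The e0_int slip affects the estimates themselves. A ratio with one intercept above the line and another below is not an inverse logit. At stake are the correct labelling of the primary error bars and the correct calculation of the primary proportions and differences.

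**Working it through.** The plan derives no figure on this point, so there is nothing to reproduce first. The inputs are the 95% level (Sections 4.2.1 and 8.1.1.1), the alpha=0.1 setting and the dummy data set (both Appendix 12).

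**1. Interval width.** A two-sided interval is estimate ± multiplier × standard error.

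- Text: 95%, multiplier z(0.975) = 1.960.
- Code: alpha=0.1, which is 90%, multiplier z(0.95) = 1.645.
- Ratio: 1.645 / 1.960 = 0.839, so the code's interval is 16% narrower. Conversely, 1.960 / 1.645 = 1.19, so moving to the stated level widens it by 19%.

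**2. Illustration on the SAP's own dummy data.** These are not trial results. Responders are 5, 9, 11, 18 and 21 out of 30 at 0, 10, 30, 100 and 200 mg. The 30 mg row is run together in the text available to me, and I read it as dose 30, 11 of 30. The logit Emax model was fitted by maximum likelihood with e0 in place of e0_int and delta-method standard errors. Degrees of freedom follow the code's rule of subjects minus three: 150 − 3 = 147. The t multipliers are then 1.976 (95%) and 1.655 (90%). The estimates are E0 = −1.488, Emax = 2.953 and ED50 = 55.3.

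| Dose | Difference from placebo | SE | 95% interval (text) | 90% interval (code) |
|---|---|---|---|---|
| 10 mg | 0.078 | 0.054 | −0.029 to 0.185 | −0.012 to 0.168 |
| 30 mg | 0.205 | 0.110 | −0.011 to 0.422 | 0.024 to 0.387 |
| 100 mg | 0.418 | 0.099 | 0.223 to 0.613 | 0.254 to 0.581 |
| 200 mg | 0.511 | 0.090 | 0.333 to 0.690 | 0.362 to 0.661 |

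For 30 mg, 0.2054 ± 1.976 × 0.1097 = 0.2054 ± 0.2168 at 95%, and 0.2054 ± 1.655 × 0.1097 = 0.2054 ± 0.1816 at 90%. The first interval includes zero and the second does not. At the other three doses the two levels agree on this.

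**3. The ESTIMATE statements.** The model sets p = exp(eta) / (1 + exp(eta)), with eta = e0 + emax × dose / (ed50 + dose). Each proportion statement computes exp(e0 + x) / (1 + exp(e0_int + x)), where x is the dose term. This equals p only if e0_int = e0, and no line in the code makes that so. There are five proportion statements (200, 100, 30, 10 and 0 mg) and four difference statements (each active dose against placebo). All nine are affected, and each difference statement contains e0_int twice.

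**4. The 60% comment.** It refers to log odds ratios. No ESTIMATE statement computes one, and no option in the code sets a 60% level, so it has no output path.

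**The case against.** The strongest reply is that the plan states only one level. The text says 95% each time the Emax analysis is mentioned, and Appendix 12 disclaims its code as an example. The ESTIMATE lines must also be repaired before they return the intended quantity, so the code cannot silently deliver a valid but too-narrow interval.

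Much of this stands. The disclaimer lowers the weight of the point, and no wrong result is shown. But it does not remove the mismatch, and it means that no amendment step would force anyone to resolve it. Repairing e0_int does not touch alpha=0.1, which sits in the procedure call. A half-repaired program would give correct estimates with 90% limits under a 95% label. The slip would be easy to miss, because the SAP uses 90% intervals by design elsewhere, for example for the mixed-model risk differences in Section 8.1.1.1.

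A reader might go further in two directions that the documents do not support:

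- **That a 60% interval would be reported.** Only a stray comment mentions it.
- **That the per-dose false-positive rate doubles from 2.5% to 5%, or that the standard of evidence loosens on the fallback path.** Sections 4.2.1 and 8.1.1.1 say the intervals are reported and presented. They do not make exclusion of zero a decision rule. The fallback error rate, "controlled at 0.05 (one-sided"), is family-wise under Hochberg, with ordered thresholds of 0.05, 0.025, 0.0167 and 0.0125. Setting it against a per-dose 2.5% compares different quantities, and for a single dose the fallback can be the stricter or the looser of the two.

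**Conclusion.** The point holds as a contradiction between text and example code in the current SAP, on the primary analysis. If the procedure call is kept, the primary intervals are 90% where 95% is promised, which is 16% narrower. If the ESTIMATE statements are kept, the nine proportions and differences are not the model's. Both consequences assume that the code is carried into production without those corrections. The documents do not show that it was, so this is a risk and not a misreported result. It is a small correction, not a flaw in the design.

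The mismatch is no reason to change any alpha level. A reader might infer that 90% intervals would be the natural partner of the one-sided 0.05 fallback. They would not be: that 0.05 is family-wise. Take four pairwise comparisons sharing one placebo arm under the global null, as a rough proxy and not the behaviour of the Emax model. At least one unadjusted 90% interval then lies above zero 14.4% of the time, against a simulated 4.2% for Hochberg.

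Nor does the point justify moving the fallback to one-sided 0.025. That would halve the Bonferroni level used for sizing, from 0.0125 to 0.00625. Taking those levels as one-sided, pooled-approximation power at 50 per arm for 43% versus 10% would fall from 94.7% to 91.0%. That would be a design decision and not a repair of this mismatch.

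**What to change.** In SAP Appendix 12:

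1. Change alpha=0.1 to alpha=0.05 in the NLMIXED call, so that parameter and ESTIMATE limits match the 95% in Sections 4.2.1 and 8.1.1.1.
2. Delete the comment that refers to a 60% interval.
3. Replace e0_int by e0 in all nine ESTIMATE statements, at both occurrences in each of the four difference statements.

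The cost is a few lines of example code. By the appendix's own terms, different production code needs no SAP amendment, so the production program can be corrected at once. The SAP text, the sample size and the error rates stay as they are.

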The binary secondary endpoints such as proportion of subjects achieving the IGA for clear (0) or almost clear (1) and ≥ 2 points improvement from baseline at all scheduled time points except Week 12, proportion of subjects with the IGA response of ≥ 2 points improvement from baseline at all scheduled time points, proportions of subjects achieving 50%, 75% and 90% reduction in EASI total score from baseline at all scheduled time points, proportion of subjects with improvement (reduction) of the pruritus NRS ≥ 3 from baseline at all scheduled time points and Proportion of subjects achieving a 50% and 75% improvement in SCORAD (SCORAD50, SCORAD75) from baseline at all scheduled time points will be analyzed using the same method specified for the primary endpoint in [Section 9.2.1](#). We will calculate estimate and 90% confidence interval for the difference of proportions (each of the active doses against placebo) using normal approximation to the distribution of the observed difference in proportions.

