8.1.1. Statistical Methods for Binary Variables

For all binary endpoints, a summary of the number of responders based on FAS with OC in each treatment arm at each time point will be produced and the response rate will also be plotted against time, by treatment group. In addition, similar tables and figures will be generated based on FAS with NR imputation for IGA response, EASI50/75/90 and NRS response.

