8.2.2.1. Analysis for the Primary Endpoint

The primary efficacy endpoint is the IGA response at Week 12. The primary analysis data will be based on FAS population with NR as missing value imputation method. Baseline is defined as the score for each assessment prior to the first dosing. .

The objective for the analysis of primary endpoint is to characterize the dose response in inducing clinical IGA reduction in subjects with moderate to severe atopic dermatitis. To achieve this objective, a three parameter Emax dose response model specified in [Section 8.1.1.1](#) will be used as the primary analysis approach to characterize the dose response relationship.

As sensitivity analyses, GLMM will be employed on IGA response from all visits including follow-up. These analyses will be carried out on the FAS population with OC as described in [Section 8.1.1.1](#). P-values and 90% confidence intervals for odds ratios between treatments and placebo will be computed at each visit. Logistic regression will be performed at each visit on FAS with NR as additional sensitivity analysis.

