8.2.2.2.2. Analysis of binary secondary endpoints

Unless otherwise stated, all primary analyses for the binary secondary endpoints are based on the FAS population with OC missing value imputation. Baseline is defined as the score for each assessment prior to the first dosing. These endpoints include:

Binary secondary endpoints include:

- *Proportion of subjects achieving the IGA for clear (0) or almost clear (1) and ≥ 2 points improvement from baseline at all scheduled time points except Week 12*
- *Proportion of subjects achieving ≥ 3 points improvement in the pruritus numerical rating scale (NRS) from baseline at all scheduled time points*
- *Proportion of subjects achieving ≥ 4 points improvement in the pruritus numerical rating scale (NRS) from baseline at all scheduled time points*
- *Proportion of subjects achieving ≥ 2 points improvement in the IGA from baseline at all scheduled time points*
- *Proportion of subjects achieving a $\geq 50\%$, 75% and 90% improvement in the EASI total score (EASI50, EASI75, EASI90) at all scheduled time points*
- *Proportion of subjects achieving a $\geq 50\%$ and 75% improvement in SCORAD (SCORAD50, SCORAD75) from baseline at all scheduled time points*

All binary secondary endpoints at each visit (except Week 12 for IGA response) will be analyzed in the same fashion as the primary endpoint using GLMM. In the case of convergence issues, logistic regression analysis at each time point with NR imputation will be performed.

For endpoint “Proportion of subjects achieving ≥ 3 points improvement in the pruritus numerical rating scale (NRS) from baseline at all scheduled time points”, subjects with baseline NRS ≤ 2 will be considered as non-responders.

For endpoint “Proportion of subjects achieving ≥ 4 points improvement in the pruritus numerical rating scale (NRS) from baseline at all scheduled time points”, only subjects with baseline NRS ≥ 4 will be analyzed.

Survival analysis will be performed for time-to-event data such as time to achieving ≥ 3 points improvement in NRS and time to achieving ≥ 4 points improvement in NRS as described in section 8.1.3.

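### SAP Appendix 13 back-transforms random-intercept GLMM logits without averaging over the random intercept, so its proportions and risk differences are not the group proportions that define the binary endpoints

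*SAP*

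**What the plan says.** **Endpoints.** Each binary endpoint in SAP section 6.1 is a proportion of subjects in a treatment group.

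**Model.** SAP 8.1.1.1 specifies a logit GLMM on observed-case (OC) data: "Random effect includes random intercept for each subject". For risk differences, "A delta method will be used to obtain 90% confidence intervals". The Appendix 11 example code has the matching random-intercept statement.

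**Back-transform.** Appendix 13 says that "using link option in GLIMMIX will generate the estimate for proportions". It sets p = exp(l)/(1 + exp(l)) from the GLIMMIX logits and treats p1 and p2 as the proportions of interest. Formulas (1) to (4) use only the logits and their covariance matrix. The random-intercept variance appears in none of them.

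**Where it applies.** SAP 8.2.2.2.2: "All binary secondary endpoints at each visit (except Week 12 for IGA response) will be analyzed in the same fashion as the primary endpoint" by GLMM. Section 8.2.2.4 says the same for PtGA response. The table in 8.2.5 marks the GLMM as the primary approach for NRS response, EASI50/75/90, SCORAD50/75 and the 2-point IGA improvement. For IGA 0/1 at visits other than Week 12 the SAP is inconsistent: 8.2.2.2.2 makes the OC GLMM the main analysis, while 8.2.5 lists it as sensitivity. For IGA response at Week 12 it is a sensitivity analysis.

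**What the protocol planned.** Protocol 9.2.2, for the binary secondary endpoints: "We will calculate estimate and 90% confidence interval for the difference of proportions (each of the active doses against placebo) using normal approximation". The SAP does not carry this interval over. It does tabulate observed rates: "a summary of the number of responders based on FAS with OC in each treatment arm at each time point will be produced".

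**The concern.** The inverse logit is non-linear. Applied to a fixed-effect logit, it gives the response probability of a subject whose random intercept is zero. The group proportion is the average of that probability over all subjects' intercepts. The two agree only if the intercept variance is zero or the probability is 0.5.

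Model-based response rates, differences from placebo and 90% intervals would therefore be reported under a label that they do not match. They would also disagree with the observed rates tabulated in the same report. The reader cannot correct for this by eye, because the size and even the sign of the discrepancy depend on the response rates and on the variance.

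**Working it through.** **Inputs.** The documents state no figure for this point, so there is none to reproduce. The planning rates are placebo 10% and active 10% + 33% = 43% (Protocol 9.1, SAP 4.2.4), for IGA response only. Two further pairs, 20% vs 60% and 10% vs 20%, are illustrations. The random-intercept SD s is assumed to be 1, 2 or 3. This corresponds to a latent within-subject correlation s²/(s² + π²/3) of 0.23, 0.55 or 0.73.

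**Step 1: what the formula targets.** For a true group proportion p, solve E[expit(η + sZ)] = p for η, with Z standard normal, by Gauss-Hermite quadrature. Appendix 13 reports expit(η). Example with s = 2: p = 0.20 gives η = −2.228 and expit(η) = 0.097; p = 0.60 gives η = 0.668 and expit(η) = 0.661. The reported difference tends to 0.661 − 0.097 = 0.564, against a true 0.40.

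| True rates | True difference | s = 1 | s = 2 | s = 3 |
|---|---|---|---|---|
| 10% vs 43% | 0.33 | 0.071/0.416, diff 0.344 | 0.032/0.386, diff 0.354 | 0.011/0.351, diff 0.340 |
| 20% vs 60% | 0.40 | 0.161/0.620, diff 0.459 | 0.097/0.661, diff 0.564 | 0.051/0.707, diff 0.656 |
| 10% vs 20% | 0.10 | 0.071/0.161, diff 0.090 | 0.032/0.097, diff 0.065 | 0.011/0.051, diff 0.039 |

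These are limits with the variance well estimated.

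**Step 2: trial-size simulation.** Two arms of 50, 9 post-baseline visits, flat rates, arm-by-visit fixed effects, no baseline covariate, Week 12 read out, 1000 runs per cell. The fit was a pseudo-likelihood of the RSPL type named in Appendix 11, in purpose-written code rather than SAS. It underestimates s (0.90, 1.61 and 2.13 at 20% vs 60%), so its results lie between the group values and the limits above.

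- *20% vs 60%:* Appendix 13 difference 0.426, 0.486, 0.526 for s = 1, 2, 3. The 90% interval covered 0.40 in 89%, 78% and 72% of runs. A separate simulation gave 0.43, 0.48, 0.53. With 20% completely random dropout, coverage was 90%, 81% and 76%.
- *10% vs 43%:* the difference moved by 0.003, 0.013 and 0.03. Reported placebo rates were 9.2%, 6.8% and 5.8%, against 10.2%, 10.5% and 11.7% observed in the same runs. Only converged runs are counted (943, 875 and 563 of 1000), because the SAP sends the others to logistic regression with non-responder (NR) imputation. In two separate sets of runs, interval coverage was about 88% to 94%.

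**Step 3: does a better fit cure it?** No. Quadrature maximum likelihood with the same Appendix 13 formula at 20% vs 60% gave 0.458, 0.557 and 0.639, with coverage 83%, 59% and 44%.

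**Step 4: do the remedies work?** At 20% vs 60%, averaging over the quadrature-estimated intercept distribution gave 0.400, 0.400 and 0.397, equal to the observed differences. Its delta-method coverage was 88.5%, 89.9% and 89.4%. The protocol's normal-approximation interval covered 88.3%, 89.0% and 89.4%. At 10% vs 43% the averaged estimate covered 91.0%, 90.8% and 90.0%.

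**The case against.** **At the only documented rates little happens.** At 10% vs 43% the difference is nearly right and the interval close to nominal. The poor coverage comes from a pair chosen for illustration. This stands, with two limits: those rates are for IGA response, and no planning rates are given for EASI50, NRS response or the other endpoints where the GLMM is the main analysis.

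**The SD is assumed, and the simulation is simplified.** At s = 1 the RSPL-type excess is only 0.026 (20% vs 60%) or 0.003 (10% vs 43%). The baseline covariate in SAP 8.1.1.1 would absorb some between-subject variance. NRS and PtGA are not collected at Week 13, so nine visits is one too many for them. All of this bears on size, not on the mechanism.

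**Readers still see group rates.** SAP 8.1.1 tabulates observed responders, with NR versions for IGA, EASI50/75/90 and NRS response, and the protocol's interval could be computed from those counts. Protocol section 9 allows the SAP to modify planned analyses. Both are true, but no interval for the group difference is planned, and the mislabelled model values remain.

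**The code may change without amendment.** Appendix 11 says so of its own example code. Appendix 13 is a stated formula without that disclaimer, and Step 3 shows that changing the fitting method does not repair it.

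**Subject-specific estimates are legitimate.** Agreed. The defect is calling them proportions and risk differences for these endpoints.

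**The odds ratios.** A reader might infer that the planned GLMM odds ratios are wrong too, because the example code names RSPL. The documents do not support adding that here: the SAP text does not require RSPL, the example may be changed freely, and the issue is separate from Appendix 13.

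**Conclusion.** The point holds: as written, Appendix 13 does not estimate the proportions of subjects that define the binary endpoints. This follows from the formula and needs only a non-zero random-intercept variance. Size and direction rest on the assumed SD of 1 to 3 and on the true rates: a negligible to small shift in the difference at 10% vs 43% with an understated placebo rate, overstatement at 20% vs 60%, understatement at 10% vs 20%.

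Three stronger readings are tempting and not supported:

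- *That the primary result is affected.* The Emax model and the NR logistic regression have no random effect.
- *That the drug effect is systematically inflated.* The sign changes with the rates.
- *That a trial decision turns on it.* Appendices 11 and 12 mention decision criteria based on differences in proportions, but no numerical criterion is given. If Emax fails, GLMM and/or NR logistic regression "may be considered for decision making to characterize the dose-response with dose being considered as a continuous variable", which is a dose-trend model. For IGA, SAP 8.2.2.1 puts the GLMM inference on odds ratios: "P-values and 90% confidence intervals for odds ratios between treatments and placebo will be computed at each visit". The affected analyses are secondary or sensitivity analyses, outside the multiplicity control in SAP 4.2.2.

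The plan should be corrected, but the consequence is one of reporting accuracy.

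**What to change.** In SAP Appendix 13 and 8.1.1.1, do one of the following.

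1. **Average before differencing.** Fit the GLMM by adaptive quadrature, average the predicted probabilities over the estimated random-intercept distribution and the baseline covariate, then take the difference, with a delta-method or bootstrap 90% interval.
2. **Relabel and supplement.** Call the current values subject-specific. Report alongside them the observed difference in proportions with the 90% interval from Protocol 9.2.2, and state whether OC or NR data are used.

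Also reconcile 8.2.2.2.2 with 8.2.5 on whether the GLMM is the main or a sensitivity analysis for IGA 0/1 at visits other than Week 12.

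**Cost.** Option 2 needs SAP wording and one standard table. Option 1 needs modest programming and a slightly more complex variance. It also needs a stated fallback when an arm-visit cell has no responders, which arose in 33 to 57 of 1000 simulated runs at 10% vs 43%, and in 74 to 104 with 20% dropout. Neither option needs new data.
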